6.5. Handling and Storage Requirements

The Investigator (or designee) is responsible for the safe and proper storage of IMP at the site. Investigational medicinal product stored by the Investigator is to be kept in a secured area with limited access according to the storage conditions mentioned on the label.

Appropriate storage conditions must be confirmed either by controlling the temperature (e.g., room, refrigeration unit) or by completion of a daily temperature log in accordance with local requirements, showing actual and minimum/maximum temperatures reached over the last 24-hour time period.

In case a temperature excursion is noted, it must be reported as per instructions contained in the EDP1815 IMP Handling Manual.

The Investigator (or designee) will instruct the participant to store the IMP at home following the instructions on the label.

6.6. IMP Accountability

An Interactive Response Technology (IRT) system will be used to record IMP dispensing and return information on a by-participant basis during the study. Details of any IMP lost, damaged (due to breakage or wastage), not used, partially used, disposed of at the study site, or returned to the Sponsor or designee must also be recorded. All supplies and pharmacy documentation must be made available throughout the study for the Sponsor (or designee) to review.

Participants will utilize an electronic diary (eDiary) to record their IMP intake on a daily basis ([Section 6.6.1 eDiary](#)).

The Investigator (or designee) is responsible for retaining all used, unused, and partially used containers of IMP until returned or destroyed.

The Investigator may assign some of the Investigator's duties for IMP accountability at the study site to an appropriate pharmacist/designee.

The Investigator must verify that the IMP is used only in accordance with the protocol.

All used (including empty containers)/partially used, unused, damaged, and/or expired IMP must be reconciled and returned to the Sponsor or designee, or it may be destroyed at the site according to applicable laws and regulations, and Sponsor SOPs, if applicable. Investigational medicinal product intended for the study cannot be used for any other purpose than that described in this protocol.

6.6.1. eDiary

The primary purpose of the diary is to enhance participant compliance with the protocol. Participants will utilize an electronic diary (eDiary) from Day -1 through to the Week 40 Follow-Up Visit. It is expected that participants will continue to use the eDiary utilized throughout the EDP1815-207 parent study. The eDiary may be either an application (app) that will be downloaded to the participant's mobile smartphone or an eDiary device specifically designated for the purpose of collecting information as described below for participants who do not have a mobile smartphone or do not wish to download an app to their phone.

Participants will be asked to capture the following information in their eDiary:

- Study IMP
 - Confirmation of dosing
 - Date and time of dosing
 - Number of capsules taken, with reasons not taken, if applicable
- Background Therapy (Emollient(s))
 - Frequency of usage (number of times a day)
- Rescue Therapy Usage
 - Confirmation of usage
- Daily Peak Pruritus Numerical Rating Scale (PP-NRS)
 - Evaluation of worst itch over previous 24-hour period
- Daily Sleep Disturbance Numerical Rating Scale (SD-NRS)
 - Evaluation of sleep quality over previous 24-hour period

Study staff will review the eDiary entries with participants at each visit. eDiaries will be reviewed for completeness and accuracy, and participants will be coached as needed on compliance with the protocol.

At the Week 40 Follow-Up or Early Termination Visit (if applicable), the study staff will assist the participants to uninstall the eDiary application on their mobile smartphone devices and/or collect any eDiary devices that were distributed to the participants.

6.7. Drug Compliance

Participants will use the eDiary to capture compliance with their study IMP. At specified visits per the Schedule of Activities (SOA), the study site staff will check numbers of used/unused capsules against diary entries and discuss with the participant the need to self-administer the capsules as directed, and to store the IMP according to label instructions.

Prior to the specified study visits per the SOA, study site staff will call participants to remind them to bring all empty/partially used IMP wallets and cartons in the original containers to the study site for their visit.

If a participant is found to be persistently noncompliant, the Sponsor, in conjunction with the Investigator, will decide as to whether the participant should be withdrawn from the study.

6.8. Dose Modification

Dose adjustments, including dose interruptions, and/or decreasing the dose frequency may be allowed for safety or tolerability after consultation with the Medical Monitor. The maximum permitted interruption at one time is 14 consecutive days and the participants should have 80% compliance with IMP administration between any two visits after allowing for permitted interruptions. In cases where IMP was interrupted for less than 14 consecutive days, but overall compliance is below 80%, the possibility for discontinuation should be discussed with the Medical Monitor.

6.9. Concomitant Medications and Treatments

Throughout the study, the participant may be prescribed concomitant medications or treatments deemed necessary to provide adequate supportive care at the discretion of the Investigator provided that the medications are licensed. However, it is the responsibility of the Investigator to confirm that details regarding the medication are recorded in full in the eCRF.

All concomitant medications and/or treatments received by a participant should be recorded on the appropriate source document and eCRF with the following minimum requirements:

- Drug trade name
- Total daily dose
- Dates of administration
- Reason for use (indication)
- Dosage information (including dose and frequency)

This will include all prescription drugs, herbal products, vitamins, minerals, over the counter (OTC) medications, and vaccines. Any changes in concomitant medications will also be recorded

in the participant's eCRF. The participant's dosing eDiary may contain information relevant to the documentation of changes in concomitant medication.

6.9.1. Permitted Concomitant Medications and Treatments

The following concomitant medications are permitted for use during the study:

- Concomitant medications for conditions other than AD may continue throughout the study, if not meeting any exclusion criteria, and should continue without change in dosage or formulation whenever possible.
- New therapy/treatments, not expected to have any impact on AD, but deemed necessary for the welfare of the participant during the study, are permitted. If there is doubt about their impact on AD or the ability of the participant to continue in the study, then this should be discussed with the Medical Monitor.
- Topical and oral antibiotics, antiviral, or antifungal therapy.
- Oral antihistamines.
- Nasal inhaled and ophthalmic corticosteroids.
- Non-replicating / non-live vaccines ([Section 6.9.3 Immunizations](#)).

All participants must use an emollient at least twice daily throughout the study ([Section 6.9.1.1 Background Therapy](#)).

6.9.1.1. Background Therapy

All participants must agree to continue with the use of an emollient at least twice daily. This must be a bland emollient which is additive-free, SLS-free, and fragrance-free and may be in cream, gel or ointment formulation. Whenever possible, the same brand and formulation of emollient should be used throughout the study by the participant. Participants are not allowed to use emollients containing additives (e.g., urea, ceramide, nicotinamide). Participants should continue this background emollient application twice daily until the Week 40 Follow-up Visit. Missed application of emollient will not be considered protocol deviation(s). On the day of the study visits, the participant will be asked to withhold the application of the emollient, and where safe, sunscreen and any other topical products until after all study assessments have been performed.

Participants will record their background therapy via the participant eDiary from Day -1 to the Week 40 Follow-Up Visit ([Section 6.6.1 eDiary](#)).

6.9.1.2. Rescue Therapy

If required, Investigators may prescribe / recommend prescription of rescue therapy for participants experiencing unacceptable worsening of atopic dermatitis. Additionally, individuals with uncontrolled atopic dermatitis could be at risk for a secondary skin infection. These participants may be prescribed an antimicrobial therapy to treat the infection as detailed below. Rescue therapy use is allowed throughout the entire study. There is no limit on the number of times that topical rescue therapy can be prescribed, although Investigators and participants may wish to consider whether the study is suitable for them if repeated courses are required.

Rescue therapy, including microbial rescue therapy, should be prescribed as detailed below, and any specific deviations should first be discussed with the Medical Monitor. Participants rescued

by such topical therapy will continue to take IMP and use of rescue therapy will be documented in the participant eDiary ([Section 6.6.1 eDiary](#)).

Between Day –1 and Week 16, rescue therapy should be as follows:

For non-sensitive body sites:

- Moderate potency (grade IV and V – [Appendix 14.1](#)) topical corticosteroids, twice daily for up to 7 days

For sensitive sites e.g., head and neck:

- Topical tacrolimus (0.1%), topical pimecrolimus (1%) or grade VII topical corticosteroid, twice daily for up to 7 days

After Week 16, participants may be prescribed topical calcineurin inhibitors and/or topical corticosteroids of any potency for up to 7 days. It is advised that the lowest effective potency topical corticosteroid is chosen.

If topical rescue therapy fails to control symptoms adequately, then the participant should be considered for alternative systemic therapy or phototherapy by the Investigator/their practitioner, at which point they will be classified as a treatment failure and IMP will be discontinued.

For possible skin infection:

- Topical:
 - Appropriate courses of topical antimicrobial therapies, such as fucidic acid cream (e.g., Fucidin), mupirocin and/or bacitracin, are acceptable for use for skin infections, as required
 - If requiring concomitant moderate potency steroid therapy, fucidic acid with betamethasone 0.1% (as the valerate ester), (e.g., Fucibet cream) twice daily for up to 7 days
- Oral:
 - Appropriate course(s) of oral antibiotic(s) may be prescribed as per clinical need

6.9.2. Prohibited Concomitant Medications and Treatments

6.9.2.1. Prohibited Concomitant Medications

Use of any of the following concomitant medications during the study require the IMP to be immediately discontinued where possible. If a participant requires treatment for atopic dermatitis with a prohibited concomitant medication during the study, they will be classified as a treatment failure. :

- Topical Corticosteroids or Topical Calcineurin Inhibitors (unless used as Rescue Therapy, [Section 6.9.1.2 Rescue Therapy](#))
- Topical PDE-4 Inhibitors
- Topical JAK Inhibitors
- Bleach baths
- Phototherapy treatment
- Tanning beds

- Systemic treatments that may lead to clinical improvements in atopic dermatitis, e.g., oral, or injectable corticosteroids, methotrexate, azathioprine, cyclosporine, mycophenolate mofetil, JAK-inhibitors, biologic therapy, and other systemic immunosuppressive therapy (note single dose intra-articular or intra-lesional corticosteroid therapy is permitted).
- Leukotriene Receptor Antagonists
- Allergen Immunotherapy
- Live (attenuated) vaccinations: not permitted at any point during the study ([Section 6.9.3 Immunizations](#)).

6.9.3. Immunizations

Non-replicating / non-live vaccines are permitted during the study. This includes all SARS-CoV-2 (COVID) non-live vaccines and non-replicating vaccines. The non-intranasal seasonal flu vaccine is permitted, as is the recombinant zoster vaccine (non-live). However, the first dose of IMP should not be taken within a 7-day window of administration of the non-live vaccine or non-replicating vaccine.

Live (attenuated) vaccinations are not permitted at any point during the study. This includes vaccines for measles, mumps, rubella, vaccinia, varicella, zoster (which contains the same virus as varicella vaccine but in much higher amount), yellow fever, rotavirus, and influenza (intranasal).

6.10. Blinding

This is an open-label extension study with all participants taking EDP1815 capsules and as such no blinding is required for the study medication in this study.

Investigators and participants will continue to be blinded to the participants treatment assignment in the EDP1815-207 parent study in order to minimize bias.

7. STUDY PROCEDURES BY VISIT

No study procedures should be performed prior to the signing of the informed consent form (ICF). The ICF will need to be signed prior to any conducting any assessments at the Day -1 visit.

Visit windows are consecutive calendar days and the target visit dates are calculated from the Day -1 visit.

The Schedule of Activity (SOA) is presented in [Table 4-1](#). An overview of each of the study assessments is presented in the subsections below. If a visit is not completed per protocol, it will be considered a missed visit. The site should still contact the participant by telephone to confirm that there have not been any adverse reactions.

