Secondary endpoints: The Eczema Area and Severity Index (EASI) Score will be utilized to measure the efficacy of EDP1815 in the treatment of atopic dermatitis. In addition to EASI, the Investigator's Global Assessment (IGA), percentage of Body Surface Area (BSA), Product of the IGA and BSA (IGA*BSA), the SCORing Atopic Dermatitis (SCORAD), the Dermatology Life Quality Index (DLQI), the Peak Pruritus Numerical Rating Scale (PP-NRS), the Sleep Disturbance Numerical Rating Scale (SD-NRS), the Patient Oriented Eczema Measure (POEM) and the Atopic Dermatitis Control Tool (ADCT) will be measured throughout the study.

The number of courses of treatment with rescue therapies; and with antibiotic treatment due to skin infection, per participant, will also be measured.

Brief Study Design: This is an Open-Label Extension (OLE) study to evaluate the long-term safety, tolerability, and efficacy of EDP1815 in participants with mild, moderate, and severe atopic dermatitis who have completed the treatment period of a prior clinical study ("parent study") with EDP1815. The parent study of this open label extension protocol is the EDP1815-207 study; A Phase 2, Multicenter, Double-Blind, Placebo-Controlled, Multiple-Cohort Study Investigating the Effect of EDP1815 in Participants for the Treatment of Mild, Moderate and Severe Atopic Dermatitis. The EDP1815-207 study will be referenced as the parent study throughout the protocol.

This study may serve as an open label extension study for future EDP1815 studies in Atopic Dermatitis.

All participants in this study will be treated with EDP1815, regardless of the treatment assignment in the EDP1815-207 study. To minimize bias, during dosing in EDP1815-208, investigators and participants will continue to be blinded to participants' treatment allocation in the parent study whilst it is ongoing. Participants in this study will be treated with EDP1815 for up to 36 weeks, followed by a follow-up visit at approximately 4 weeks after the end of treatment.

Interim safety and efficacy analyses may be performed throughout the study as required for ongoing evaluation of the benefit-risk profile for EDP1815. These may include either all participants enrolled in the study or use of a subset of participants who transitioned to this study from a specific parent study. Interim analyses may also incorporate data collected within the parent Atopic Dermatitis EDP1815 studies which feed into this study.

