2. STUDY OBJECTIVE(S)

2.1. Primary Objectives

The primary study objective is to evaluate the long-term safety and tolerability of EDP1815 in the treatment of atopic dermatitis. The primary endpoints to measure this objective will be the incidence and rate per 100 patient-years of treatment-emergent adverse events during the 36-week treatment period and the 4-week follow-up period of this study, and during the treatment period of this study and the relevant parent study.

TEAEs will be defined as all events starting after first dose of study drug and on or before 28 days after last dose for each participant. All TEAEs will be included in the assessments of incidences and rates, regardless of compliance with study medication, use of other medications or deviations from the study protocol.

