4.5. Schedule of Study Assessments

Table 4-1: Schedule of Assessments

Procedure	Initial Visit (Parent study End of Treatment Visit)	36- Week Treatment Period							End of Study Visit	Early Termination Visit ^o
		Day	Week	Visit window (days)						
Day	-1	1	28	56	84	112	168	252	280	
Week	0	1	4	8	12	16	24	36	40	
Visit window (days)	--	--	+/-3	+/-3	+/-3	+/-3	+/-7	+/-7	+3	
Informed consent ^a	X									
Inclusion and exclusion criteria	X									
Medical history and current medical conditions (including smoking status) ^b	X									
Full Physical examination ^c	X*							X		X
Brief Physical Examination ^c			X	X	X	X	X		X	
Weight ^d	X*		X	X	X	X	X	X	X	X
Height ^d	X									
Pregnancy test ^e	X*		X	X	X	X	X	X	X	X
12-lead ECG ^f	X*		X	X	X	X	X	X	X	X
Laboratory assessments (hematology, biochemistry, urinalysis) ^g	X*		X	X	X	X	X	X	X	X

Procedure	Initial Visit (Parent study End of Treatment Visit)	36- Week Treatment Period							End of Study Visit	Early Termination Visit ^o
		1	28	56	84	112	168	252		
Day	-1	1	28	56	84	112	168	252	280	
Week	0	1	4	8	12	16	24	36	40	
Visit window (days)	--	--	+/-3	+/-3	+/-3	+/-3	+/-7	+/-7	+3	
Biomarker (blood) collection: Inflammation immune surveillance in circulation								X		X
Biomarker (blood) collection: Immune protein markers								X		X
Vital signs ^b	X*		X	X	X	X	X	X	X	X
Participant diary (eDiary) ^l	X		X	X	X	X	X	X	X	X
Randomization (EDP1815-207 Cohort 3) ^j	X									
Dosing ^k		X	—————→							
IMP Accountability			X	X	X	X	X	X	X	X
vIGA ¹	X*		X	X	X	X	X	X	X	X
BSA involvement (%) ¹	X*		X	X	X	X	X	X	X	X
EASI ¹	X*		X	X	X	X	X	X	X	X
SCORAD ¹	X*		X	X	X	X	X	X	X	X
POEM	X*		X	X	X	X	X	X	X	X
PP-NRS ^m	X*		—————→							X

Procedure	Initial Visit (Parent study End of Treatment Visit)	36- Week Treatment Period							End of Study Visit	Early Termination Visit ^o
		Day	28	56	84	112	168	252		
Day	-1	1	28	56	84	112	168	252	280	
Week	0	1	4	8	12	16	24	36	40	
Visit window (days)	--	--	+/-3	+/-3	+/-3	+/-3	+/-7	+/-7	+3	
SD-NRS ^m	X*	—————→								X
ADCT	X*		X	X	X	X	X	X	X	X
DLQI	X*		X	X	X	X	X	X	X	X
Digital Photographs ⁿ	X*		X	X	X	X	X	X	X	X
Telephone Call ^o										X
AE SAE Review ^p	X	—————→								X
Concomitant Medication Review	X	—————→								X

[figure not shown]
*Assessments performed at the End of Treatment Visit of the parent study that do not need to be repeated if this visit occurs on the same day as the Initial Visit of the OLE (Day -1).

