- ^k Study medication will be dispensed after all Day -1 activities are completed and if the participant is confirmed as eligible to participate in the study. The participant will be instructed to take the first IMP dose on Day 1 at home. The capsules are to be taken once daily at approximately the same time each day. On study visit days, dosing may occur at home prior to the study visit. Participants should refrain from consuming acidic drinks 1 hour either side of dosing and from eating 2 hours before dosing and 1 hour after dosing. Participants will be required to record their daily dosing in the eDiary.
- ^l AD Investigator rating scales. Participants will be asked to withhold all emollients, sunscreens, or moisturizers on the day of these study visits until all study assessments are completed.
- ^m The Pruritus-NRS (worst itch) and the Sleep Disturbance-NRS (SD-NRS) scale will be asked daily from the Day-1 Visit to the Week 40 or Early Termination Visit (if applicable) via the participant eDiary.
- ⁿ Digital photographs should be taken of the upper and lower body (upper & lower anterior and upper & lower posterior) as half body shots. Additional close-up photographs of up to six specific body areas (i.e., limbs, trunk and back) may also be taken. The same sites photographed in the parent study should be followed throughout this study for each participant.
- ^o Participants who withdraw from the study early will have an Early Termination Visit. If due to treatment failure, this visit should be arranged within 72 hours of the start of any new AD therapy, when possible. The participant will also be asked to have a final telephone call 28 days (+3 days) after taking their last dose of IMP for safety assessments. The date of this telephone call will be considered the end of study date for these participants.
- ^p Adverse Events (AE) and Serious Adverse Events (SAE) will be captured from the time the participant signs the informed consent.

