7.3. Week 40 Follow Up/ End of Study Visit

This visit will be the last visit in the study and will take place approximately 4 weeks after the last dose of IMP. Prior to this visit, the participant will be asked to withhold the application of the emollient, and where safe, sunscreen, and any other topical products until after all study assessments have been performed. See [Section 6.9.1.1 Background Therapy](#).

The following procedures will be performed:

- Brief physical examination
- Vital signs including weight measurements
- 12-lead ECG
- Urine sample collection for pregnancy testing (women of childbearing potential only)
- Blood sample collection for safety labs
- Urine sample collection for urinalysis
- Digital photographs of the same lesions/body area taken at the Day -1 Visit
- AD rating scales - vIGA, EASI (and BSA), and SCORAD
- Patient reported clinical rating scales – POEM, DLQI and ADCT
- Collection and or review of PP-NRS and SD-NRS scores in participant diary
- Review of and documentation of concomitant medications and therapies including emollient use
- Assessment and documentation of adverse events (AEs)
- Removal of eDiary application from smartphone/ collection of eDiary device

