7.6.4. COVID-19 Mitigation Steps

If a participant with COVID-19 must self-isolate or quarantine while on study, and a study visit coincides with this self-isolation or quarantine, the study visit will be missed and the reason the visit was not done recorded in the source documents with COVID-19 isolation / lockdown as the reason for the visit not completed.

In lieu of the study visits, the participant should receive a telephone call to assess adverse reactions, ascertain study IMP status (i.e., did the participant self-interrupt taking IMP) and emollient usage, and collect information on any concomitant medications, including any rescue therapy. Information should be recorded in the participant's source documents and entered into the EDC, as applicable.

The participant must try and attend all study visits; however, the Week 16 and Week 36 study visit should not be missed wherever possible. These visits, therefore, may be conducted outside of the protocol study window. Please contact the Medical Monitor to discuss further.

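### Two anchors for the Week 40 visit: timed from Day -1, a completer's last scheduled safety contact can fall 21 days after last dose, before the TEAE window closes

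*Protocol*

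**What the plan says.** **Anchor on Day -1.** Protocol Section 7 states: "Visit windows are consecutive calendar days and the target visit dates are calculated from the Day -1 visit". It makes no exception for Week 40. Table 4-1 gives Week 36 as Day 252 with a ±7-day window and Week 40 as Day 280 with a one-sided +3-day window.

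**Anchor on last dose.** Protocol Section 7.3 says of the Week 40 visit: "This visit will be the last visit in the study and will take place approximately 4 weeks after the last dose of IMP". The Protocol Summary agrees, describing treatment "followed by a follow-up visit at approximately 4 weeks after the end of treatment".

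**What the contact has to cover.** Protocol Section 2.1 counts TEAEs that start "on or before 28 days after last dose for each participant". SAP Section 5.3.4.2 extends the limit to 30 days, a change declared in SAP Table 9.

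**Early terminators.** Table 4-1 footnote o, repeated in Section 7.4, times their last contact from dosing: "The participant will also be asked to have a final telephone call 28 days (+3 days) after taking their last dose of IMP for safety". Completers have nothing scheduled after Week 40.

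**Out-of-window Week 36 visits.** Section 7.6.4 says of the Week 16 and Week 36 visits: "These visits, therefore, may be conducted outside of the protocol study window". It does not say how Week 40 is then timed.

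**The concern.** The primary endpoint is the incidence and rate of TEAEs over a window that closes a fixed number of days after each participant's own last dose. The last scheduled contact for completers is, on one reading, fixed to the study calendar instead. The two agree only when the last dose falls near Day 252. A site that follows Table 4-1 after a late Week 36 visit holds the final visit before the window closes. A site that follows Section 7.3 may have to breach the Table 4-1 window to reach four weeks.

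Adverse events are elicited by a standard question at each study visit (Protocol Section 9.4.1). If the final visit comes early, nothing scheduled prompts a report of events in the remaining days. Early terminators are asked at 28 to 31 days after last dose, so ascertainment of the primary endpoint could depend on whether a participant completed the study.

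**Working it through.** **Inputs**
- Week 36 window: 252 ± 7 = Day 245 to 259, which is 15 days (Table 4-1).
- Week 40 window: 280 to 280 + 3 = Day 280 to 283, which is 4 days (Table 4-1).
- Last dose of a completer: taken as the day of the Week 36 visit. Protocol Section 5.4 treats permanent stopping before that visit as early discontinuation, Section 7.2 allows dosing at home on visit days, and SAP Section 5.3.4.2 ends the completer's Treatment Phase at that visit.
- TEAE limit: 28 days (Protocol Section 2.1) or 30 days (SAP Section 5.3.4.2).

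**Step 1: the plan's own figure.** On nominal days, 280 − 252 = 28 days, or 4 weeks. This reproduces the intended follow-up.

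**Step 2: permitted range.** Follow-up = Week 40 day − Week 36 day.
- Shortest: 280 − 259 = 21 days.
- Longest: 283 − 245 = 38 days.
- With Week 36 on Day 259, Week 40 falls 21, 22, 23 or 24 days after last dose. If the last dose was taken the day before that visit, the figures are 22 to 25.

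**Step 3: when the window closes after the last contact**

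| | 28-day limit | 30-day limit |
|---|---|---|
| Day 280 too early if Week 36 is on | Day 253-259 | Day 251-259 |
| Even Day 283 too early if Week 36 is on | Day 256-259 | Day 254-259 |
| Largest shortfall | 28 − 21 = 7 days | 30 − 21 = 9 days |
| Short combinations, Week 40 on Day 280, 281, 282, 283 | 7 + 6 + 5 + 4 = 22 of 60 | 9 + 8 + 7 + 6 = 30 of 60 |

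The last row counts permitted combinations (15 × 4 = 60). It is not a probability, because the documents give no distribution of visit dates.

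**Step 4: an on-time completer.** Week 36 on Day 252 and Week 40 on Day 280 give 28 days. That meets the protocol limit and is 30 − 28 = 2 days short of the SAP limit, with no late visit involved.

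**Step 5: size in context.** The worst shortfall is 7/28 = 25% of the post-dose window, or 9/30 = 30% under the SAP. Measured against the whole TEAE period of such a participant, it is 7/(259 + 28) = 7/287 = 2.4%, or 9/(259 + 30) = 9/289 = 3.1%.

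**Step 6: alternative reading of dosing.** If dosing stopped at Day 252 whatever the visit date, follow-up would be 280 − 252 = 28 to 283 − 252 = 31 days. The 28-day shortfall disappears. Against 30 days, a visit on Day 280 or 281 remains 2 or 1 days short.

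**The case against.** The strongest reply is that the documents already lean towards the safe timing. Section 7.3 and the Protocol Summary both place the visit about four weeks after dosing ends, and the one-sided +3 window resembles the early-terminator call. A site that waits until day 28 incurs at most a logged deviation, because SAP Section 7.7 keeps out-of-window data in the tables. For an out-of-window Week 36 visit, Section 7.6.4 directs the site to the Medical Monitor. All of this is fair, but it shows an unresolved conflict rather than resolving it: Section 7 states the Day -1 anchor without exception.

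Second, the 21-day figure depends on dosing continuing to a late Week 36 visit. The Protocol Summary speaks of up to 36 weeks, and Sections 6.1 and 6.2 of 36 weeks in total, which can be read as a cap at Day 252. This stands as a condition on the result (Step 6). Section 5.4 and the SAP point the other way, and these passages need to be reconciled.

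Third, a reader might infer that events at the end of the window are never collected, or that SAEs and abnormal laboratory values are missed in completers but captured in early terminators. The documents do not support either inference:
- Section 9.4 exempts SAEs from reporting only beyond 30 days after last dose, and that duty is not tied to a visit.
- Section 9.5.5 excludes new AEs from the eCRF only when they start more than 28 days after the final dose.
- The early terminators' day-28 contact is a telephone call, with no blood sample. Completers have laboratory tests at both Week 36 and Week 40.

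Fourth, SAP Table 9 records that the study was terminated early, and the reduced outputs omit rates. The number of affected completers may therefore be small. TEAE incidence and event counts for this study's own period are still retained, and the protocol says it may serve as the extension for future studies.

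**Conclusion.** The point holds as a conflict over which anchor times the completers' last safety contact, with a bounded effect on ascertainment of the primary endpoint. If dosing runs to the Week 36 visit and Table 4-1 governs, in-window follow-up is 21 to 38 days and cannot reach 28 days when Week 36 falls on Day 256-259. Under the SAP's 30 days, the nominal schedule is itself 2 days short.

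What is missing is a scheduled prompt, so the events at risk are late and mainly non-serious. The text supports saying that these may be missed in some completers. It does not support saying that they will be missed, or that the loss extends to laboratory findings. The frequency cannot be estimated, because the documents give no data on how often Week 36 runs late. The change is worth making because it is cheap and concerns the primary endpoint.

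**What to change.** Reconcile Section 7, Table 4-1 and Section 7.3 by anchoring the completers' last safety contact to the last dose. That contact can be the Week 40 visit itself. Alternatively, keep the visit day and add a call of the footnote-o type for any completer whose visit is held too early. State that the anchor still applies when Week 36 is held out of window under Section 7.6.4.

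Set the contact no earlier than the close of the TEAE window actually used:
- **28 days (protocol):** footnote o's 28 (+3) days is sufficient. For a last dose on Day 259, the contact falls on Day 287 to 290.
- **30 days (SAP):** footnote o is not sufficient, since a contact on day 28 or 29 is still too early. The completers' contact, the early-terminator call and the 28-day eCRF cut-off in Section 9.5.5 must all be moved to match. For a last dose on Day 259, the earliest contact is Day 289.

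**Cost:** one footnote in Table 4-1 and one sentence in Section 7, plus the matching edits if 30 days is kept. Some end-of-study visits move by about a week (287 − 280 = 7 days at most under 28 days, 289 − 280 = 9 under 30), or a short call is added. The 40-week maximum in Section 4.2 would need a qualifying word, since Day 287 is 287/7 = 41 weeks.
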